e)	Imaging evidence of traumatic head injury
2.	Associated, immediately following the head injury, with at least one:
a)	Transient confusion, disorientation or impaired consciousness
b)	Loss of memory for events immediately before or after injury
c)	Two or more of: nausea, vomiting, visual disturbance, dizziness/vertigo, impaired memory/concentration, gait instability
C.	Headache is reported to have developed within 7 days after one of:
1.	The injury to the head
2.	Regaining consciousness following injury to the head
3.	Discontinuation of medication(s) that impair the ability to sense or report headache following injury to the head
D.	If headache persists for >3 months following onset then it is "persistent" PTH. If headache resolved within 3 months of onset or 3 months have not yet passed, then it is "acute" PTH.
E.	Not better accounted for by another ICHD-3 diagnosis

- PTH onset 7- 56 days prior to the time of enrollment
- Adults 18-70 years of age
- Willing to receive erenumab treatment
- Willing to maintain a headache diary
- Willing and able to return for follow-up visits

Additional Inclusion Criteria for the Clinical Trial (assessed after run-in phase)

- 4 or more moderate or severe headache days during the 4-week run-in phase

- An increase of at least 2 moderate to severe headache days compared to pre-TBI
- At least a 30% increase in moderate to severe headache days compared to pre-TBI
- At least 80% compliant with diary keeping during the 4-week run-in phase (i.e. provides data on at least 80% of days)

Exclusion Criteria

- Chronic headache (i.e. at least 15 headache days/month for more than 3 months) within 12 months prior to the mTBI that led to the current PTH, including PPTH, chronic migraine, medication overuse headache, new daily persistent headache, hemicrania continua, chronic tension-type headache.
- Diminished decision-making capacity that in the investigator's opinion would interfere with the person's ability to provide informed consent and complete study procedures
- Started or changed dose of a headache preventive medication within the 3 months prior to screening.
- Use of onabotulinumtoxinA in the head, neck or face region within 6 months of screening
- During the 6 months before screening, use of opioids or barbiturates on an average of at least 4 days per month

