Additional Inclusion Criteria for the Clinical Trial (assessed after run-in phase)

- 4 or more moderate or severe headache days during the 4-week run-in phase
- An increase of at least 2 moderate to severe headache days compared to pre-TBI
- At least a 30% increase in moderate or severe headache days compared to pre-TBI
- At least 80% compliant with diary keeping during the 4-week run-in phase (i.e. provides data on at least 80% of days)

Exclusion Criteria

- Chronic headache (i.e. at least 15 headache days/month for more than 3 months) within 12 months prior to the mTBI that led to the current PTH, including PPTH, chronic migraine, medication overuse headache, new daily persistent headache, hemicrania continua, chronic tension-type headache.
- Diminished decision-making capacity that in the investigator's opinion would interfere with the person's ability to provide informed consent and complete study procedures
- Started or changed dose of a headache preventive medication within the 3 months prior to screening.
- Use of onabotulinumtoxinA in the head, neck or face region within 6 months of screening
- During the 6 months before screening, use of opioids or barbiturates on average at least 4 days per month
- Subjects who underwent an intervention or used a device (e.g., nerve blocks, transcranial magnetic stimulation, vagal nerve stimulation, or electrical trigeminal nerve stimulation) for headache within 3 months of screening.
- History of major psychiatric disorder such as schizophrenia and bipolar disorder

- History or evidence of any unstable or clinically significant medical condition, that in the opinion of the investigator, would pose a risk to subject safety or interfere with the study evaluation, procedures, or completion
- Pregnancy
- Breastfeeding
- History of myocardial infarction, stroke, transient ischemic attack, unstable angina, coronary artery bypass surgery, or other revascularization procedures within 12 months prior to screening.

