
during the open label extension were similar to that observed in the double-blind phase and comparable to placebo.

Hypothesis/Objective

The objective of this study is to collect hypothesis generating data about whether intervention with erenumab is an effective treatment for PTH attributed to mTBI. Participants will receive erenumab when PTH has been present for 35-84 days. Once PTH has been persistent for this period of time, patients may be less likely to remit or improve spontaneously compared to if they were enrolled earlier after PTH onset. Thus, this population of individuals with PTH would be considered in high need of treatment.

Specific Aims/Study Endpoints

Primary endpoint

- Moderate-to-severe headache day frequency measured at weeks 9-12 after administration of first dose of erenumab 140mg vs. frequency of moderate-to-severe headache days during the 4-week baseline phase (BP). A moderate-to-severe headache day is defined as any headache lasting at least 2 hours and which at any point reaches at least moderate intensity.

Secondary endpoints

- Percentage of patients with at least a 50% reduction in headache days during weeks 9-12 after administration of first dose of erenumab 140 mg compared to BP.
- Percentage of patients with chronic headache defined as ≥ 15 headache days during weeks 9-12 after administration of first dose of erenumab 140mg compared to BP.
- Headache Impact Test (HIT-6) at weeks 9-12 after administration of first dose of erenumab 140 mg compared to BP.
- Acute treatment day frequency measured at weeks 9-12 after administration of first dose of erenumab 140mg compared to BP. (Acute treatment day is any day on which an analgesic, triptan, or ergotamine containing medication is taken, or device neuromodulation [e.g. vagal or trigeminal nerve electrical stimulation or single pulse transcranial magnetic stimulation] is administered to relieve headache)

Methods

This is a phase II prospective, open-label clinical trial of a CGRP receptor mAb for treatment of PTH. Of note, this was originally designed as a randomized, placebo-controlled clinical trial. However, recruitment into the clinical trial was slow. Since the estimated total enrollment would

be inadequate for making comparisons between the placebo and erenumab groups, the study was revised to an open-label design.

[figure not shown]

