Individuals with PTH will be receive monthly subcutaneous administration of erenumab 140 mg over a 3-month period (total of 3 injections). The primary endpoint will be the mean number of moderate-to-severe headache days between 9-12 weeks after treatment vs. the number of moderate-to-severe headache days during the 4-week BP. Subjects will maintain an electronic daily diary during the 4-week BP, for the 12 weeks post-first treatment, and during weeks 21-24 post-first treatment.

All participants in this clinical trial will complete baseline and follow-up questionnaires described in detail in the separate human studies protocol subtitled "Individual Projects Excluding Clinical Trial" within the "Phenotyping and Neurophysiology" section. In brief, the following questionnaires will be used to collect baseline and follow-up data:

- 1) TBI and PTH characteristics
- 2) Post-TBI symptoms using the 22-item Symptom Evaluation Checklist from the Sport Concussion Assessment Tool (SCAT)
- 3) Headache Impact Test (HIT-6)
- 4) Self-Rating Questionnaire on Hypersensitivity to Sound
- 5) Photosensitivity Assessment Questionnaire
- 6) Allodynia Symptom Checklist (ASC-12)
- 7) State Trait Anxiety Inventory (STAI)
- 8) Beck Depression Inventory (BDI)
- 9) Posttraumatic Stress Disorder Checklist
- 10) Survey of Autonomic Symptoms
- 11) Pain Catastrophizing Questionnaire
- 12) Insomnia Severity Index
- 13) Cognitive Function
- 14) Dizziness Handicap Inventory
- 15) Trail Making Test A and B
- 16) Controlled Oral Word Association Test (COWAT)
- 17) Global Impression of Change
- 18) Follow-up Headache Characteristics
- 19) Adverse Events
- 20) Sensory Testing Results *not applicable for Rochester and Florida sites
- 21) Vital Signs
- 22) Pregnancy Test Results

In addition, all research participants will maintain a daily electronic headache and symptom diary to provide data on headaches, treatment, and presence and severity of associated symptoms. The diary will be maintained for the first 4 weeks, starting with enrollment (i.e. first research visit) and through week 16 (i.e. third research visit), and again during weeks 21-24 post-first treatment. The electronic diary requires individuals to record whether they did or did not have a headache each day, the severity of their pain, headache duration, level of functional disability due to the headache, and use of medication. To optimize compliance with diary maintenance, the amount of

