For patients who are participating in the clinical trial, no preventive therapy for headache should be started. Preventive therapies include drugs, biologics, devices, procedures, and non-pharmacological modalities.

Statistical Plan:

Sample Size- all individuals who qualify for the clinical trial and are interested in participating will be enrolled, up to a maximum of 112 participants. This sample size is empirical and results will be used for hypothesis generation.

Headache Diary - Values for missing calendar day entries in a given month will be imputed by prorating scores of 4-week post-treatment periods with 20–27 days of diary data. For months with less than 10 days of diary data, scores will be estimated by the substitution of the patient's previous 28-day period mean score, multiplied by the ratio of the mean for all patients in the same period and divided by the mean for all patients in the previous period. For post-treatment periods with 10–19 days of diary data, scores were estimated using a mean of both methods.

Outcomes - Efficacy analyses will be conducted in the full analysis set, which includes all subjects (intent-to-treat population) who received at least one dose of study drug and have at least 10 days of efficacy assessments for the primary endpoint measured during weeks 9–12. Safety analyses will be performed in all subjects who receive at least one dose of study drug. The primary and secondary endpoints will be analyzed using a within-person one-sample t-test. Signed rank test will be used for the primary analysis if there is a deviation from normality assumption as assessed by Shapiro Wilk's test. Confidence intervals will be calculated. SAS version 9.4 (SAS Institute, Cary NC) will be used for all statistical analyses.

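### The plan scales incomplete follow-up diaries to 28 days but states no such scaling for baseline; read literally, this understates the improvement, probably by a small amount.

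*Combined protocol and SAP*

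**What the plan says.** The Headache Diary paragraph of the Statistical Plan has three tiers.

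- **20–27 recorded days:** "Values for missing calendar day entries in a given month will be imputed by prorating scores of 4-week post-treatment periods with" that many days.
- **10–19 days:** "For post-treatment periods with 10–19 days of diary data", the score is the average of the prorated and the substituted value.
- **Under 10 days:** "For months with less than 10 days of diary data", the plan substitutes the patient's "previous 28-day period mean score, multiplied by the ratio of the mean for all patients in the same period" over the corresponding mean for the previous period.

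The entry criteria for Path A/D and for Path C both ask for a patient to be "At least 80% compliant with diary keeping during the 4-week run-in phase".

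The primary endpoint is described in two ways. Specific Aims/Study Endpoints sets weeks 9–12 "vs. frequency of moderate-to-severe headache days during the 4-week baseline phase (BP". Methods sets the weeks 9–12 mean against "the number of moderate-to-severe headache days during the 4-week BP". Outcomes in the Statistical Plan specifies a within-person one-sample test, and the trial is open-label with no control arm.

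**The concern.** A patient may enter with an incomplete baseline diary, and every admissible incomplete baseline falls inside the 20–27 day band that the plan prorates at follow-up. Proration is nevertheless attached to post-treatment periods. The 10–19 day tier is also post-treatment only, and the under-10 tier cannot apply to an eligible baseline. On the literal reading, the two halves of a before–after comparison are on different scales.

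With no control arm, nothing cancels a scaling error in the baseline. It carries into the primary change, the 50% responder rate, the comparison of chronic headache with baseline, and acute treatment days. HIT-6 is not a count of days and is unaffected. Two programmers working from this text could obtain different primary estimates from the same data.

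**Working it through.** The plan has no figure of its own to reproduce: the maximum of 112 participants is called empirical, and no effect size or standard deviation is given.

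**Step 1: which baselines are affected.** 0.80 × 28 = 22.4. So 22 days (78.6%) fails, 23 days (82.1%) passes, and 23–27 recorded days is admissible but incomplete.

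**Step 2: shortfall per affected patient.** With d recorded days and missing days that resemble recorded ones, the expected raw count is B × d/28, where B is the full 28-day count. The expected shortfall is 1 − d/28.

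| Recorded days d | 27 | 26 | 25 | 24 | 23 |
|---|---|---|---|---|---|
| Expected shortfall | 3.6% | 7.1% | 10.7% | 14.3% | 17.9% |
| Proration factor 28/d | 1.037 | 1.077 | 1.120 | 1.167 | 1.217 |

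Example: 10 headache days in 23 recorded days in both periods. Follow-up becomes 10 × 28/23 = 12.17. Against a raw baseline of 10, that is an apparent worsening of 2.17 days where nothing changed. With both periods scaled, the change is zero.

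**Step 3: direction.** A raw count cannot exceed the full 28-day count. Leaving baseline raw can therefore only lower it, and so can only shrink an apparent reduction.

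**Step 4: size across the cohort.** The documents give neither diary completion nor expected headache frequency, so both are assumed. Let p be the daily completion. For independent missed days, d follows Binomial(28, p). For clustered missed days, d follows a beta-binomial with intraclass correlation ρ, that is, parameters p(1/ρ − 1) and (1 − p)(1/ρ − 1). Both are restricted to d ≥ 23. The mean shift is B × E[1 − d/28 | d ≥ 23], with B = 12 assumed.

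| Assumed completion | Incomplete baselines, independent | Mean shift, independent | Incomplete baselines, ρ = 0.2 | Mean shift, ρ = 0.2 |
|---|---|---|---|---|
| 98% | 43% | 12 × 2.0% = 0.24 day | 13% | 0.12 day |
| 95% | 76% | 12 × 4.96% = 0.60 day | 30% | 0.28 day |

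At ρ = 0.1 the shifts are 0.18 and 0.41 day. Clustering reduces the effect because the 23-day entry rule removes the worst diaries. Under independence, the shift is 0.16–0.40 day for an assumed baseline of 8 and 0.32–0.79 for 16. At 90% independent completion it would be 9.2%, or 1.11 days for a baseline of 12, and 5.5% of run-in patients would fail the diary criterion.

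For an assumed baseline of 12 and a true 50% reduction (6.0 days), the estimate would be 6.0 − 0.24 = 5.76 or 6.0 − 0.60 = 5.40 days under independence. Under clustering it would be 5.88 or 5.72.

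**Step 5: binary endpoints.** In expectation, the true reduction that corresponds to an apparent 50% is 1 − 0.5 × d/28, which is 51.8% (27 days) to 58.9% (23 days). The true frequency that corresponds to a raw count of 15 is 15 × 28/d, which is 15.6 to 18.3 days. These are averages and not cut-offs for a patient, because counts are whole days. With 12 true headache days and one of 28 days missed at random, the raw baseline is exactly right with probability 16/28 = 57%, and otherwise is 11. With 15 true headache days and one day missed, the patient still counts as chronic with probability 13/28 = 46%.

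**The case against.** The strongest reply is that nothing in the plan says baseline stays a raw count. The rule opens with any given month, the endpoint is called a frequency in both periods, and the substitution tier uses a previous 28-day score, which for the first post-treatment month is the baseline. Methods does speak of a number of baseline days, but it uses the same noun for follow-up, which is prorated. A reader might infer that the plan deliberately prescribes mismatched scales. The documents do not support that. They leave the baseline rule unstated, and the mismatch arises on the literal reading only. The gap stands all the same, because the only proration that is written down is post-treatment.

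Second, the effect is modest and conservative, and the study is hypothesis-generating. Entry requires 80% of run-in days, daily entries are designed to take under two minutes, payment depends on 80% completion, and compliance is monitored. At an assumed standard deviation of change of 5–8 days and the maximum n = 112, the 95% half-width is 1.96 × SD/√112, about 0.9–1.5 days, which exceeds the shifts at 98% and 95% completion. This limits the importance of the point. It does not remove it, since a systematic shift does not average out and the effect estimate is the main product of the trial.

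Third, proration can err the other way. If only headache-free days are skipped, the raw baseline is correct and scaling overstates it by 28/d − 1, which is 3.7% (27 days) to 21.7% (23 days) in affected patients. Averaged over the cohort, that is 2.1% at 98% and 5.4% at 95% independent completion. This would favour benefit, and the documents do not show which pattern applies. The risk is real, but the plan already accepts the same assumption for follow-up, and an unscaled sensitivity analysis would expose it.

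**Conclusion.** The concern holds in a limited form. Proration is stated for post-treatment periods only, eligible baselines may have 23–27 recorded days, and no rule in the text provided scales them. On the literal reading the comparison is biased against benefit in every endpoint counted in days. The expected understatement of baseline is 3.6% to 17.9% in affected patients; those with 28 recorded days are untouched. Over the cohort it is probably small: about 0.1 to 0.6 day at an assumed baseline of 12 and an assumed completion of 95–98%, depending on how far missed days cluster. Completion nearer 90% would make it larger.

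These sizes rest on assumed completion, assumed headache frequency and missing days that resemble recorded ones. Two stronger inferences should be resisted. The gap cannot by itself produce a false signal of benefit. Nor does every affected patient have to exceed a 50% reduction to count as a responder. Confidence is medium, because the sponsor may have meant the rule to cover both periods.

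**What to change.** Extend the proration rule to *4-week baseline and post-treatment periods*, so that baseline counts with 23–27 recorded days are multiplied by 28/(days recorded) for every endpoint counted in days. Leave the run-in entry criteria unchanged. Report the distribution of recorded baseline days, and give the primary result with the unscaled baseline as a sensitivity analysis.

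The cost is a few words in the Statistical Plan, one line of code, one small table and one additional analysis. The downside is that the proration assumption now applies to baseline too; the sensitivity analysis shows how much the result depends on it.

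### The averaging rule for 10–19 diary days in weeks 9–12 adds avoidable error and, mainly at 15–19 days, can give scores that the recorded days rule out

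*Combined protocol and SAP*

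**What the plan says.** The Headache Diary paragraph of the Statistical Plan sets three rules according to the number of diary days in a four-week period.

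- 20–27 days: the score is "imputed by prorating scores of 4-week post-treatment periods with 20–27 days of diary data".
- Under 10 days: "scores will be estimated by the substitution of the patient's previous 28-day period mean score". That value is then rescaled by a group ratio: the current period's all-patient average over the one before it.
- 10–19 days: "For post-treatment periods with 10–19 days of diary data, scores were estimated using a mean of both methods".

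The text gives no cap at 28, no floor at the days recorded and no ceiling at recorded plus missing days.

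Under Outcomes, the full analysis set takes patients who were dosed and "have at least 10 days of efficacy assessments for the primary endpoint measured during weeks 9–12". For the weeks 9–12 window, analysed patients are therefore outside the under-10 rule but inside the 10–19 rule.

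Two secondary endpoints turn the diary score into a yes/no result: "Percentage of patients with at least a 50% reduction in headache days during weeks 9-12" and "Percentage of patients with chronic headache defined as ≥ 15 headache days during weeks 9-12". Neither has its own missing-data rule.

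**The concern.** The under-10 rule produces a score for a whole period. Averaging it with proration gives weeks 5–8 half of the weeks 9–12 score, however much of weeks 9–12 was recorded. With 19 of 28 days in hand that weight is still 50%; at 20 days it drops to zero. Recorded days are not held as fact, so the result can contradict them.

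What is at stake is the accuracy of individual scores for patients in this band. Those scores enter the primary endpoint, the two binary headache-day endpoints and, if the diary rule is meant to cover them, acute treatment days.

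**Working it through.** **Inputs.** From the Headache Diary paragraph: proration = 28x/d; substitution S = P × R, taken as a 28-day total; score for d = 10–19 = 0.5 × (28x/d + S). The true count must lie between x and x + (28 − d). The plan gives no value for R, no expected diary completeness and no variance, so there is no plan figure to reproduce.

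**When the bounds break.** Proration alone stays within bounds for every d from 10 to 27. For the average:

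- Score below x when 14x/d + S/2 < x, that is S < 2x(d − 14)/d. This needs d of at least 15. At d = 19 it is S < 0.526x.
- Score above x + 28 − d when S > 56 − 2d + 2x(d − 14)/d. At d = 19 it is S > 18 + 0.526x. For d = 10–14 it requires S above 28, which the uncapped rule allows if R exceeds 1.

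With R = 1 the largest breach, in either direction, rises from 1 day at d = 15 to 5 days at d = 19. For example, at d = 19, x = 19 with S = 0 scores 14, and x = 0 with S = 28 scores 14 when at most 9 days are possible.

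**Worked cases at d = 19, R = 1** (P and baseline chosen for illustration; last column is the score when only missing days are imputed):

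| x | P | Score by the plan | Possible range | Consequence | Missing days only |
|---|---|---|---|---|---|
| 15 | 4 | 0.5 × 22.1 + 2 = 13.1 | 15–24 | scored below 15 although 15 days are recorded | 19.2 |
| 5 | 23 | 3.68 + 11.5 = 15.2 | 5–14 | scored chronic although 14 is the maximum | 9.9 |
| 0 | 24 | 0 + 12 = 12.0 | 0–9 | baseline 20: scored a 40% reduction, although at least (20 − 9)/20 = 55% is certain | 3.9 |
| 11 | 3 | 8.11 + 1.5 = 9.6 | 11–20 | baseline 20: scored a responder although 11 days are recorded | 14.1 |

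A contradiction at the 15-day cut-off needs a sharp change between months. For whole-number S at d = 19, it takes S of 7 or less with at least 15 days recorded, or S of 23 or more with a maximum possible count below 15.

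**Weight on the previous period.** Plan: 50% for every d from 10 to 19. Imputing only missing days: 0.5 × (28 − d)/28, which is 32% at d = 10 and 16% at d = 19.

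**Simulation of the 10–19 day band.** All inputs are assumed: beta-distributed daily headache probability with mean 0.30 or 0.45 and concentration 1.5–6, correlation between successive periods 0.5–0.95, R = 1, days missing at random; 24 scenarios.

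- Impossible scores: about 1–11% of the band, depending strongly on the assumed spread.
- Root-mean-square error against the true 28-day count: 2.1–4.9 days under the plan, 1.7–2.8 with missing days only. The latter was lower in every scenario.
- Misclassification at 15 days: 6–18% against 4–12%.
- Classification at 15 days contradicted by the patient's own recorded days: at most 0.8% of the band.
- Mean error: about 0.00–0.01 day under either rule when period means are equal.

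A separate run (previous-period mean 8–16 days, R 0.8–1.0, correlation 0.3–0.9) looked at 15–19 day patients alone. About 1–17% scored below their recorded days, about 0–10% above the possible maximum, and 0–1.4% had a 15-day classification contradicted by their records. No contradiction rate was computed for the 50% endpoint; for that endpoint the evidence is the worked cases.

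**The case against.** **Another reading exists.** The paragraph opens by speaking of imputing values for missing diary entries. If both methods fill only the missing days, their mean is essentially the rule proposed here and the problem disappears. Against that, the later sentences speak of estimating the period's score, and the substituted quantity is a whole-period score. The whole-period reading is the more natural one, but the ambiguity is real, and clarification may be all that is needed.

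**The band may be small.** Trial entry requires at least 80% diary compliance in the run-in, compliance is monitored with prompt contact, and payment is tied to 80% completion. This does not show that the band is empty, but no trial-level effect can be claimed.

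**The worked cases are extreme.** They use 19 recorded days, where the breach is largest, and abrupt reversals between adjacent months. This stands: they prove that the rule can fail, not that it often does.

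**Stronger readings are tempting.** A reader might infer that impossible scores arise throughout the band, that they cause the 6–18% misclassification, or that the primary result is biased. None of these is supported. For 10–14 days only an uncapped S above 28 breaks a bound. Most misclassification is ordinary imputation error near the cut-off, and 4–12% remains after the fix. Under missing at random the rule adds noise without shifting the mean. Recorded days are down-weighted, not discarded.

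**The fix is not uniquely best.** It keeps the arbitrary 0.5, and its previous-period weight still steps from 16% at 19 days to zero at 20. Plain proration had lower error in several lower-correlation scenarios (for example 1.89 against 2.59 days). Both points stand; even so, the fix beat the plan's rule in all 24 scenarios.

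**Conclusion.** The point holds within limits. That the rule can return impossible scores is a matter of algebra and needs no assumption beyond the whole-period reading. That it adds avoidable error across the band is shown only by simulation, and the rates there rest on inputs that the documents do not supply. The loss is in the precision of individual scores and in classification near the cut-offs. Direct contradictions with a patient's own diary should be uncommon, and no bias in the primary endpoint has been demonstrated. The number of patients with 10–19 diary days is not stated, so the effect on the trial's results is unknown. For an open-label, single-arm trial meant to generate hypotheses, this is a low-to-moderate priority correction.

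**What to change.** For 10–19 diary days, replace the average of whole-period scores with

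score = x + (28 − d) × 0.5 × (x/d + min(P × R/28, 1)).

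Recorded days stay as recorded and the score always lies between x and x + (28 − d). The 20–27 day rule already has this form, since 28x/d = x + (28 − d) × x/d, and needs no change. At minimum, bound every score between x and x + (28 − d). If filling only the missing days was always intended, the Headache Diary paragraph should state this formula so that the text has one reading.

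The cost is one formula in the plan and a few lines of SAS code, with no new data and no patients lost. Reporting how many analysed patients fall in the 10–19 day band would let readers judge how much the choice matters.
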